b An unscheduled visit may be performed at any time at the patient's request or per investigator's discretion. Only mandatory procedures are specified; additional assessments per clinical discretion. In addition, unscheduled urgent safety laboratory samples may be collected at the discretion of the investigator or medical monitor at any time to assist with further investigations of cardiovascular events or other clinical event of interest. The samples should be collected as soon as possible in association with the event.

c For the purpose of scheduling study visits, a week is defined as 7±2 days.

d It is anticipated that few patients will require visits beyond week 120, however the number of visits required will depend on order and duration of enrollment. After week 168, further visits occur every 12 weeks until completion. If necessary, the visit at week 180 would have identical procedures to week 132, the visit at week 192 would have identical procedures to week 144. If a visit beyond week 192 is necessary, contact Sponsor for guidance.

e In addition, an evaluation should take place as soon as possible for patients already in the study, following approval of Global Amendment 2.

f Vital signs include temperature, pulse and blood pressure. Weight will be measured at all visits.

g Anemia panel includes blood smear, serum iron, ferritin, total iron binding capacity, folic acid, haptoglobin, IL-1, IL-6, IFN- $\gamma$ , TNF- $\alpha$ , and hepcidin. Assessed at baseline and also at 1 subsequent time point (with B12) if hemoglobin decrease of >1 g/dL from the patient's hemoglobin level at baseline and the decrease is confirmed.

h Serum chemistry (including electrolytes, fibrinogen, glucose, urea, creatinine, alanine aminotransferase, aspartate aminotransferase, gamma-glutamyl transpeptidase, alkaline phosphatase, creatine phosphokinase, C-reactive protein, pancreatic amylase [lipase will be tested in case of abnormal pancreatic amylase results], total protein, albumin, direct and total bilirubin) and complete blood count (CBC) with differential. Coagulation to be tested only if required according to Guidance on Safety Monitoring.

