      - anemia panel (blood smear, serum iron, ferritin, total iron binding capacity, folic acid, haptoglobin, IL-1, IL-6, IFN- $\gamma$ , TNF- $\alpha$ , and hepcidin) and B12

- additional investigations and follow-up per the investigator's discretion or sponsor's request
- Serum chemistry (including electrolytes, fibrinogen, glucose, urea, creatinine, liver enzymes, CPK, CRP, pancreatic amylase, total protein, albumin, direct and total bilirubin).
- estimated GFR\*
- Fasting lipid profile at week 48 and every 48 weeks until completion/ET.
- Serum TSH, T3, and free T4 at week 24 and every 24 weeks until completion/ET.
- Blood samples for potential biomarker measures will be collected at weeks 24 and 48.
- Pharmacokinetic study: blood samples for analysis of laquinimod plasma concentrations will be collected at weeks 4, 8, 12, 24 and 48.\*
- Ascertain use of acceptable contraception.\*
- All patients will undergo brain and cervical spinal cord MRI scans without Gd at weeks 24 and 48.
  - Weeks 24 and 48 MRI will be performed within 14 days of the clinical visit.
  - In case of steroid treatment, study MRI should be performed before such treatment or delayed to allow a minimum of 14 days but not more than 28 days from the completion of the steroid course.
- EDSS and FSS will be performed every 12 weeks until completion/ET visit (if applicable)
- T25FW, 9HPT, and SDMT will be performed every 12 weeks until completion/ET visit (if applicable). At week 48 and every 48 weeks thereafter, SDMT will be performed as part of the BICAMS assessment.
- mRS will be evaluated at week 72.
- BICAMS, including SDMT, will be evaluated at week 48 every 48 weeks thereafter.
- LCVA will be assessed at week 24 and every 24 weeks until completion/ET.
- MSWS-12 will be performed at week 12 and every 12 weeks until completion/ET.
- Evaluation and management of major modifiable cardiac risk factors (with referral to treatment and follow-up in suitable clinic if needed) will be performed at weeks 96 and 144.
- Ancillary studies:
  - CSF (to be performed in selected sites) will be collected from all patients who signed an appropriate, EC approved informed consent form, at week 48 (see Section 8.4.1 for further details of the assessments).

- OCT evaluation (to be performed in selected sites) will be performed in all patients who signed an appropriate, EC approved informed consent form, at weeks 48 and 96 to assess retinal thickness.

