3. STUDY DESIGN

3.1. General Design and Study Schema

This is a multinational, multicenter, randomized, double-blind, parallel-group, placebo-controlled study, to evaluate the efficacy, safety and tolerability of daily oral administration of laquinimod (0.6 or 1.5 mg) in patients with PPMS.

On 30 December 2015 the Data Monitoring Committee (DMC) for the CONCERTO and ARPEGGIO studies held an unscheduled meeting to review cardiovascular events. The DMC found an imbalance in serious cardiovascular events in the high dose treatment arms (1.2 mg in CONCERTO, 1.5 mg in ARPEGGIO): in CONCERTO there were 6 such cases in the 1.2 mg arm but none in the 0.6 mg or placebo arms, along with a myocardial infarction in the ARPEGGIO 1.5 mg dose group and a cerebral infarction in a 31-year old patient in the 1.2 mg arm of CONCERTO. Due to these events and the DMC recommendation to stop all laquinimod treatment arms above 0.6 mg in the MS trials, the 1.5 mg treatment arm in the ARPEGGIO study was discontinued as of 01 January 2016.

Prior to 01 January 2016, eligible patients were randomized in a 1:1:1 ratio into 1 of the following treatment arms:

1. Laquinimod 0.6 mg daily
2. Laquinimod 1.5 mg daily- in total 95 patients were randomized to this arm.
3. Daily placebo

As of 01 January 2016, following a decision to discontinue the laquinimod 1.5 mg dose arm, additional eligible patients who are enrolled will be randomized in a 1:1 ratio into one of the following treatment arms:

1. Laquinimod 0.6 mg daily
2. Daily placebo

A capped randomization procedure will be employed to ensure that the proportion of Expanded Disability Status Scale (EDSS) 6.0 and 6.5 patients will not exceed more than 20% of all enrolled patients.

The study will include screening up to 6 weeks and 2 parts: Part A (core study) and Part B (data analysis).

Part A will last at least 48 weeks, and individual patients will experience variable treatment durations, depending on the order of enrollment.

Once the last ongoing patient completes the week 48 visit, the sponsor will declare end of Part A and begin performing study analyses.

[figure not shown]

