5.3. Multiple Comparisons and Multiplicity

The overall significant level for this study is 5%, using two-tailed tests and/or two-sided confidence intervals with 95% confidence level. In order to protect the study from type-I error inflation, the secondary endpoints will be interpreted inferentially only if a statistically significant treatment effect is detected in the primary analysis. Type-I error will be further controlled by employing the Hierarchical Approach, (i.e. each secondary endpoint will be analyzed only in case the preceding endpoint will have a p-value less or equal to 0.05) according to the following order:

1. Time to CDP as measured by EDSS

2. Time to CDP event as measured by EDSS or T25FW
3. Change from baseline to week 48 in the T25FW test
4. The number of new T2 lesions at week 48

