5.6. Study days and visit windows

Study days will be numbered relative to the 1st day of study drug administration. The start of treatment (day 1) is defined as the date on which a patient takes the 1st dose of study drug. Days will be numbered relative to study start (i.e., ..., -2, -1, 1, 2, ...; with day 1 being the start of study drug and day -1 being the day before the start of study drug). No windows schemes will be applied to the data.

For by-visit summaries, if there are multiple assessments at a post baseline time point then the last non-missing assessment at that visit will be used for the summary.

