7.4. Secondary Efficacy Variables and Analysis

7.4.1. Time to CDP as measured by EDSS.

Time to CDP will be defined as increase in EDSS of ≥ 1 point from baseline EDSS, if EDSS at entry is ≤ 5.0 or increase of ≥ 0.5 point, if EDSS at entry is ≥ 5.5 . This increase should be confirmed after at least 12 weeks. Progression cannot be confirmed during a protocol defined relapse.

To calculate the time of CDP, the following algorithm will be used:

Let E_t be an EDSS measurement of the patient under consideration observed at time (measured by weeks from the patient's baseline date).

Let E_0 be the baseline EDSS measurement for that patient.

Let $s = t + 12$.

The time to CDP for the patient under consideration is defined as t if all the following conditions hold:

1. If $0 \leq E_0 \leq 5$ then let $\Delta = 1$. Otherwise, let $\Delta = 0.5$.
2. $E_t \geq E_0 + \Delta$.
3. For any $t < q_1 < s$, if the patient's EDSS was evaluated at time q_1 , then $E_{q_1} \geq E_0 + \Delta$
4. $E_{q_2} \geq E_0 + \Delta$ for some $q_2 \geq s$, and at time q_2 , the patient was not experiencing a relapse (i.e. q_2 is not between onset and stabilization date of a relapse).
5. t is the earliest time point during the study in which conditions 2-4 hold.

If no such t exists, then the time to confirmed progression will be right censored by the patient's last EDSS evaluation date from Part A (or part B if the data from both part A and part B is used for analysis) of the study. In case time t exists without fulfilling conditions 3 and 4 because time q_2 is after the patient completed Part A (or part B if the data from both part A and part B is used for analysis) of the study (or performed ET), and therefore cannot be seen, then the right censored will be on time t and not in the last EDSS evaluation.

If a patient died due to MS disease progression, then this patient will be analyzed as having CDP and the time to CDP will be calculated using the onset date of progression.

If a patient died due to MS before having progression, then the time to disability progression will be censored using the date of death.

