7.4.2. Time to CDP event as measured by EDSS or T25FW

Time to CDP as measured by EDSS or T25FW will be defined by reaching at least 1 of the following 2 types of event for each individual:

- An increase from baseline in EDSS score (≥ 1 point from baseline EDSS, if EDSS at entry is ≤ 5.0 or increase of ≥ 0.5 point, if EDSS at entry is ≥ 5.5), confirmed after at least 12 weeks, **or**
- An increase of at least 20% from baseline in the T25FW test, confirmed after at least 12 weeks

Progression cannot be confirmed during a protocol defined relapse. A similar algorithm to that described for CDP as measured by EDSS will be used for definition and censoring rules of this variable (see Section 7.4.1).

T25FW will be calculated as a mean time of two T25FW trials at each visit. In cases when a patient could not complete a T25FW trial due to the physical limitations a value of 180 seconds will be assigned for that trial (this is the maximal possible value for the T25FW test).

Time to CDP as measured by EDSS or T25FW, confirmed after at least 12 weeks will be analyzed using the ITT population and will include data from all the study assessments done up to seven days after the date of last dose of the study drug (all the following assessments will be excluded from this analysis). This analysis will be performed using baseline adjusted Cox's proportional hazards regression model (SAS® PROC PHREG) in which 1 contrast for comparing laquinimod 0.6 mg to placebo will be constructed. In addition to treatment group, categorical EDSS at baseline (≤ 4.5 or > 4.5), age at baseline, T25FW at baseline, natural logarithm of T2 lesion volume at baseline, and CGR will be used as covariates. The SAS code for this analysis is as follows:

```

PROC PHREG;
  CLASS ARM EDSSBASE CGR;
  MODEL TIME_TO_PROGRESSION*CENSOR(1,2,3)=ARM EDSSBASE T25BASE AGE LT2BASE CGR /
COVB RL;
  CONTRAST 'Laq 0.6 to Plb' ARM 1 / ESTIMATE=EXP;
  WHERE ARM in ('Laquinimod 0.6 mg', 'Placebo'); RUN;

```

In case the above model will not converge due to CGR variable, then CGR will be removed from the model.

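### The 12-week CDP rule ignores a reversal recorded at or after t + 12 weeks, so an unsustained rise can count as progression dated before the reversal

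*SAP*

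**What the plan says.** SAP 7.4.1 and Protocol 9.6.2 give the same algorithm. Time is "measured by weeks from the patient's baseline date" and s = t + 12. Condition 2 needs EDSS at or above baseline plus delta at t. Condition 3 needs the same at any assessment strictly between t and s. Condition 4 needs it at some assessment q2 at or after s that is not during a relapse. By condition 5, t "is the earliest time point during the study in which conditions 2-4 hold". Nothing requires q2 to be the first assessment at or after s.

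Protocol 3.11.3 schedules EDSS every 12 weeks, the same length as the confirmation interval. SAP 5.6 adds: "No windows schemes will be applied to the data".

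For the EDSS-or-T25FW endpoint, SAP 7.4.2 states: "A similar algorithm to that described for CDP as measured by EDSS will be used for definition and censoring rules of this variable". SAP 7.5.3 (1-of-4), 7.5.4 (24-week) and 7.5.20 (T25FW only) refer back to the same algorithm. Under SAP 5.3 the EDSS endpoint stands first among the secondaries, and "each secondary endpoint will be analyzed only in case the preceding endpoint will have a p-value less or equal to 0.05".

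**The concern.** Condition 3 is there to reject a rise that goes away again. With visits 12 weeks apart, the visit most likely to show that falls at about s, where the check stops. If it falls on or after s, a return below threshold is recorded but has no effect, and any later raised reading confirms the event and dates it at the first one. If it falls a day before s, the same clinical course is rejected at t.

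Two things follow. Transient readings can become events, and a genuine later progression can be dated to an earlier transient reading. SAP 7.5.4 describes the 24-week version as an increase that must be sustained, so ignoring recorded reversals is unlikely to be intended. The endpoints at stake are the first two secondaries and the exploratory endpoints that reuse the rule.

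**Working it through.** **Inputs.** The conditions come from SAP 7.4.1, the 12-week schedule from Protocol 3.11.3, and actual dates from SAP 7.4.1 and 5.6. The study-procedures tables define a scheduling week as 7±2 days without saying how that accumulates. I therefore take visit scatter of ±c days with c = 2, 5 or 24 (24 being 2 days for each of 12 weeks). The documents give no rate of transient readings, so p = 5% and 10% are assumptions. They also give no CDP event rate, hazard ratio or power, so there is no stated figure to reproduce.

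**One patient.** Raised on day 84 (t), below threshold on day 168, raised on day 252. Then s = 84 + 84 = 168. Day 168 is not strictly before s, so condition 3 passes. Day 252 meets condition 4, and the event is dated day 84. Move the middle visit to day 167 and condition 3 fails, so there is no event at day 84.

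**Nominal weeks 12, 24, 36, 48** (1 = at or above threshold, no relapse). No scheduled visit lies strictly between t and t + 12, so any two raised visits make an event: 6 + 4 + 1 = 11 of 16 patterns. A sustained rule needs two adjacent raised visits: 8 of 16. The three extra patterns are 1010, 1001 and 0101. Pattern 1011 is an event under both rules, but is dated week 12 as written and week 36 if sustained.

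**Actual dates.** With each visit day uniform over ±c days, the chance that two consecutive visits are at least 84 days apart is g = (1 + 1/(2c+1))/2. This is 0.600, 0.545 and 0.510 for c = 2, 5 and 24. It is also the share of raised–normal–raised courses counted at the first reading. Visits two apart always exceed 84 days (at least 168 − 48 = 120).

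| Pattern | P(event), as written | P(event), sustained |
|---|---|---|
| 1100, 0110, 0011 | g each | g each |
| 1010, 0101, 1001 | g each | 0 |
| 1110, 0111, 1111 | 1 each | 1 each |
| 1101 | 1 | g |
| 1011 | 1 − (1 − g)² | g |

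Assume independent transient readings at rate p, no true progression, and q = 1 − p:

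- As written: 6g·p²q² + [3 + 1 − (1 − g)²]·p³q + p⁴
- Sustained: 3g·p²q² + (2 + 2g)·p³q + p⁴

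For c = 5 (g = 6/11) and p = 0.10, p²q² = 0.0081 and p³q = 0.0009:

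- As written: 3.273 × 0.0081 + 3.793 × 0.0009 + 0.0001 = 0.0300
- Sustained: 1.636 × 0.0081 + 3.091 × 0.0009 + 0.0001 = 0.0161

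For p = 0.05, p²q² = 0.002256 and p³q = 0.000119, which gives 0.0078 against 0.0041.

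| False CDP, four visits | p = 5%: written / sustained | p = 10%: written / sustained |
|---|---|---|
| ±2 days | 0.9% / 0.4% | 3.3% / 1.8% |
| ±5 days | 0.8% / 0.4% | 3.0% / 1.6% |
| ±24 days | 0.7% / 0.4% | 2.8% / 1.5% |
| Nominal weeks | 1.4% / 0.7% | 5.2% / 2.8% |

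For scale, with the SAP's 140 patients per arm and ±5 days, the excess is 140 × (0.0300 − 0.0161) ≈ 2 false events per arm at 10%, and 140 × (0.0078 − 0.0041) ≈ 0.5 at 5%.

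**24-week endpoint.** Here s = t + 24, so the visit 12 weeks after t lies inside condition 3 and is checked. Only a reversal at or after t + 24 weeks escapes: on nominal weeks, pattern 1101 is still an event dated week 12. At 10% and ±5 days, false events over four visits are 0.16% as written against 0.11% sustained.

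**The case against.** The rule is prespecified, the same in both arms and scored by blinded raters, in a Phase 2 proof-of-concept study whose primary endpoint is MRI-based. The plan also limits noise. The same Examining Neurologist should see a patient throughout, and the Neurostatus guidance in Protocol Appendix G does not let EDSS steps up to 4.0 change without a functional-system change. The 24-week endpoint is a partial check, and the patient listings would expose reversals. All of this stands. It limits the weight of the point but does not close the gap.

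A reader might infer four stronger things that the documents do not support:

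- **A false treatment effect.** Nothing in the rule favours either arm.
- **A blocked hierarchy.** Dilution of the EDSS endpoint could matter for the three endpoints below it. But the size depends on a CDP rate, a hazard ratio and a misreading rate (in both directions) that the documents do not give, so no power loss can be stated.
- **A much larger problem in the main analysis.** The gap does widen with follow-up, and SAP 3.1 says "individual patients will experience variable treatment durations, depending on the order of enrollment". But eight visits means week 96. Protocol Amendment History gives 49 patients enrolled by 1 July 2015 and 301 by 1 February 2016, or (301 − 49)/7 = 36 a month. If that pace held, the remaining 375 − 301 = 74 would enter by about early April 2016, and Part A would end 48 weeks later, about March 2017. A patient enrolled on 1 July 2015 would then be near week 88. So fewer than 49 of 375 (13%) could have eight Part A visits, some of them in the 1.5 mg arm, which is excluded from inference. The combined Part A and B repeats are exploratory.
- **A 24-week rule with no persistence check.** It does check the visit 12 weeks after t.

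**Conclusion.** The point holds as a defect in the written rule. Visits from t + 12 weeks up to the confirming visit are unchecked, and whether a raised–normal–raised course counts at its first reading can turn on one day of visit timing. That conclusion, the 11-against-8 count and the mis-dating of pattern 1011 follow from the text alone.

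The percentages are illustrative. They rest on assumed transient rates of 5 and 10%, independence between visits, no true progression and four visits. Under those assumptions the written rule gives a little under twice the false CDP of a sustained rule, but the absolute excess is small: about 0.4 and 1.4 percentage points at ±5 days. The expected consequence is modest dilution and mis-dating of the first two secondary endpoints and the exploratory endpoints that reuse the rule. The 24-week endpoint is affected least. The correction is worth making because it is cheap and the rule as written can count the wrong events and dates.

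**What to change.** In SAP 7.4.1, before unblinding, replace conditions 3 and 4 with a single condition: there is an assessment q2 at least 12 weeks after t, not during a protocol-defined relapse, and EDSS is at least E0 + delta at every assessment from t through q2. Use 24 weeks for the 24-week endpoint. Apply the same rule, with the matching thresholds, to the EDSS-or-T25FW, 1-of-4 and T25FW-only endpoints. List the change in SAP section 12, since Protocol 9.6.2 carries the same algorithm and the SAP prevails where the two differ.

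The cost is one rewritten condition and a programming change, with no new data. There will be somewhat fewer CDP events, and a genuine progressor with one falsely normal reading will be dated later or missed. The 84-day minimum stays, so a two-visit rise whose second visit comes at day 83 is unconfirmed under either rule. This change is not meant to alter that.

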### **3.11.6. Unscheduled Visit**

An unscheduled visit may be performed at any time during the study at the patient's request or as deemed necessary by the investigator. The date and reason for the unscheduled visit will be recorded.

The reasons for the unscheduled visit may be:

- a new adverse event or an adverse event follow-up
- change in concomitant medications
- possible relapse
- relapse follow-up
- laboratory follow-up
- study drug dispensing, accountability and/or replacement
- patient compliance
- repeat MRI scan
- other

If the visit is related to a relapse, this will be clearly indicated on the CRF and the Examining Neurologist will carry out a complete neurological evaluation (EDSS and FSS).

Mandatory unscheduled visit procedures (except for patients that perform the unscheduled visit for repeat MRI scan):

Placebo-Controlled Study – Multiple Sclerosis  
Clinical Study Protocol with Global Amendment 02 Study TV5600-CNS-20006 (ARPEGGIO)

- vital signs
- evaluation of adverse events
- review of concomitant medications
- ascertain use of acceptable contraception.

Additional clinical procedures may be performed by the Treating Neurologist to assure patient safety, and must be recorded in the source documentation.

According to the judgment of the investigator or medical monitor, the following unscheduled procedures may be performed:

- urgent safety laboratory test panel (see Section [7.3.4](#))
- collection of unscheduled pharmacokinetic blood sample
- collection of sample for potential biomarker analysis

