Time to CDP as measured by EDSS confirmed after at least 12 weeks will be analyzed using the ITT population and will include data from all the study assessments done up to seven days after the last dose of the study drug (all the following assessments will be excluded from this analysis). This analysis will be performed using a baseline adjusted Cox's proportional hazards regression model (SAS® PROC PHREG) in which 1 contrast for comparing laquinimod 0.6 mg to placebo will be constructed. In addition to treatment group, categorical EDSS at baseline (≤ 4.5 or > 4.5), age at baseline, natural logarithm of T2 lesion volume at baseline, and CGR will be used as covariates. The SAS code for this analysis is as follows:

```

PROC PHREG;
  CLASS ARM EDSSBASE CGR;
  MODEL TIME_TO_PROGRESSION*CENSOR(1,2,3)=ARM EDSSBASE AGE LT2BASE CGR / COVB RL;
  CONTRAST 'Laq 0.6 to Plb' ARM 1 / ESTIMATE=EXP;
  WHERE ARM in ('Laquinimod 0.6 mg', 'Placebo');
RUN;

```

In case the above model will not converge due to CGR variable, then CGR will be removed from the model.

The adequacy of the proportional hazards assumption will be confirmed by including a time-dependent covariate of laquinimod 0.6 mg (as dummy variables) by log (time) interaction in the analysis model and testing it at the 5% level. In case the proportional hazards assumption will

be rejected, the log rank test (SAS® PROC LIFTEST) will be used for statistical inference. The SAS code for checking the proportional hazards assumption is as follows:

```
PROC PHREG;
  CLASS ARM EDSSBASE CGR;
  MODEL TIME_TO_PROGRESSION*CENSOR(1,2,3)=ARM ARMT EDSSBASE AGE LT2BASE CGR ;
    ARMT = ARM*log(TIME_TO_PROGRESSION);
    PROP_HAZARDS_TEST_LAQ_0_6: test ARMT;
    WHERE ARM in ('Laquinimod 0.6 mg', 'Placebo');
  RUN;
```

In case the above model will not converge due to CGR variable, then CGR will be removed from the model.

In addition, patients with CDP will be summarized using descriptive statistics. The time to CDP will be presented by Kaplan-Meier curves stratified by treatment group.

EDSS scores and changes from baseline to each visit will be summarized using descriptive statistics.

All analyses presented in the section will be repeated to include both part A and part B when the study is completed.

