Time to CDP as measured by at least 1 of 4 types of events for each individual will be analyzed using the same methods as described for time to CDP as measured by EDSS in Section 7.4.1. In addition to treatment group, categorical EDSS at baseline (≤ 4.5 or > 4.5), age at baseline, natural logarithm of T2 lesion volume at baseline, T25FW at baseline, 9HPT at baseline, SDMT score at baseline and CGR will be used as covariates.

In case the above model will not converge due to CGR variable, then CGR will be removed from the model.

The adequacy of the proportional hazards assumption will be checked using the same methodology as described for time to CDP as measured by EDSS in Section 7.4.1.

In addition, patients with CDP as measured by at least 1 of 4 types of events will be summarized using descriptive statistics. The time to CDP as measured by at least 1 of 4 types of events will be presented by Kaplan-Meier curves stratified by treatment group.

All analyses presented in the section will be repeated to include both part A and part B when the study is completed.

7.5.4. Time to CDP as measured by EDSS confirmed after at least 24 weeks.

Similar algorithm to that described for CDP as measured by EDSS confirmed after at least 12 weeks will be used for definition and censoring rules of this variable (see Section 7.4.1) with the distinction that the increase in EDSS should be sustained for at least 24 weeks instead of 12 weeks. The methodology and covariates for this analysis will be the same as for the primary analysis, including check of the proportional hazards assumption.

In addition, patients with CDP as measured by EDSS confirmed after at least 24 weeks will be summarized using descriptive statistics. The time to CDP as measured by EDSS confirmed after at least 24 weeks will be presented by Kaplan-Meier curves stratified by treatment group.

All analyses presented in the section will be repeated to include both part A and part B when the study is completed.

7.5.5. The number of new T1-hypointense lesions at week 48

The number of new T1-hypointense lesions at week 48 will be analyzed by applying the same methodology used to analyze the number of new T2 lesions at week 48 (see Section 7.4.4). Natural logarithm of baseline T2 lesion volume covariate will be replaced by natural logarithm of T1-hypointense lesion volume at baseline. In addition, the number of new T1-hypointense lesions at week 48 will be summarized using descriptive statistics.

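### The Cox code for the disability-progression endpoints names no tie method and the time unit is left open; the default pulls the hazard ratio slightly toward 1, and naming Efron costs nothing.

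*SAP*

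**What the plan says.** **Code.** SAP 7.4.1 analyses CDP by EDSS with "MODEL TIME_TO_PROGRESSION*CENSOR(1,2,3)=ARM EDSSBASE AGE LT2BASE CGR / COVB RL". SAP 7.4.2 (EDSS or T25FW) uses "MODEL TIME_TO_PROGRESSION*CENSOR(1,2,3)=ARM EDSSBASE T25BASE AGE LT2BASE CGR" with the same two options, COVB and RL. The proportional-hazards check models in both sections carry no options. The by-gender EDSS model in 7.5.21 also has no TIES option.

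**Cross-references.** Sections 7.5.3, 7.5.4 and 7.5.20 print no code and rely on earlier methods. In 7.5.3, for example: "Time to CDP as measured by at least 1 of 4 types of events for each individual will be analyzed using the same methods".

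**Assessment times.** Protocol 3.11.3 states "EDSS and FSS will be performed every 12 weeks until completion/ET visit (if applicable"), and T25FW follows the same interval. Protocol 3.11.6 adds EDSS off schedule: at a relapse-related unscheduled visit "the Examining Neurologist will carry out a complete neurological evaluation (EDSS and FSS"). Protocol 6.4.10.1 describes relapses as rare in this disease.

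**Time scale.** In SAP 7.4.1 EDSS is "observed at time (measured by weeks from the patient's baseline date"), and censoring uses evaluation dates. SAP 5.6 adds: "No windows schemes will be applied to the data". Nothing says whether time in weeks is a decimal or a whole number.

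**The concern.** With no TIES option, PROC PHREG uses the Breslow approximation. That is software knowledge and is not stated in the documents. When several patients have an event at the same time, Breslow keeps all of them in the risk set for each of those events, which shrinks the log hazard ratio. Efron uses the same data and removes most of that shrinkage.

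The two endpoints with printed code stand first and second among the secondary endpoints in SAP 5.3. Each later endpoint is tested only if the one before it has p of at most 0.05, so power lost at the first step carries down the chain. If the tie method were revisited after unblinding, it would be a post-hoc choice between two hazard ratios.

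**Working it through.** **The plan's own figure.** The only power stated is for the primary endpoint, PBVC (Protocol 9.2): difference 0.3, SD 0.8, 126 evaluable per arm, two-sided 5%.
- 0.3 / (0.8 × √(2/126)) = 0.3 / 0.1008 = 2.98, and Φ(2.98 − 1.96) = 84.5%, against 84% stated.
- 252 / (1 − 0.10) = 280, as stated.

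No event count, event rate, hazard ratio or power is given for CDP in this trial, so the effect of ties has to be simulated under assumptions.

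**Formula.** At a time with d tied events, let S be the sum of exp(βx) over the risk set and D the same sum over the d patients with events.
- Breslow subtracts d × log S from the log partial likelihood.
- Efron subtracts the sum over l = 0, …, d − 1 of log(S − (l/d) × D).

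The two agree when d = 1. Both were fitted to the same simulated data sets.

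**Inputs from the documents.** 140 per arm (SAP 3.3); 12-weekly detection; at least 48 weeks of follow-up, varying by patient (SAP 3.1); an onset counts only if a visit 12 weeks later exists.

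**Assumptions.**
- Last visit at weeks 48 to 120; exponential hazards; no other covariates.
- Placebo progression by week 48 of 10%, 20%, 35% or 50%.
- Hazard ratio 0.5, 0.66 or 0.8. The middle value is 1 − 0.34, from the pooled relapsing-remitting result in Protocol 1.1.1.
- Visits exactly on the nominal week, or scattered uniformly by ±2 or ±14 days. The documents define a scheduling week as 7±2 days but fix no window for a 12-weekly visit.
- 400 runs per setting, 36 settings.

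**Results at true hazard ratio 0.66** (Breslow vs Efron hazard ratio; ratio of log hazard ratios; power in %):

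| Placebo progression | All times on nominal week | ±2 days | ±14 days |
|---|---|---|---|
| 10% | 0.667 vs 0.665; 0.991; 17.2 vs 18.0 | 0.628 vs 0.627; 0.998; 21.5 vs 21.5 | 0.663 vs 0.663; 1.000; 19.3 vs 19.3 |
| 20% | 0.665 vs 0.659; 0.980; 35.0 vs 36.0 | 0.660 vs 0.659; 0.996; 36.5 vs 36.7 | 0.662 vs 0.662; 0.999; 40.5 vs 40.5 |
| 35% | 0.674 vs 0.664; 0.962; 54.0 vs 56.0 | 0.666 vs 0.664; 0.992; 55.2 vs 55.7 | 0.669 vs 0.668; 0.999; 56.8 vs 56.8 |
| 50% | 0.683 vs 0.666; 0.938; 64.7 vs 69.3 | 0.664 vs 0.660; 0.987; 70.5 vs 71.3 | 0.654 vs 0.654; 0.998; 73.3 vs 73.3 |

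The comparison to read is Breslow against Efron within a cell. Levels differ between cells partly through simulation error.

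**Across all three hazard ratios.**
- Nominal weeks (8 to 9 distinct event times): ratio 0.932 to 0.992, so attenuation of about 1 to 7%. Power loss is 0 to 6 points; the largest is 32.5 − 26.3 = 6.2 points, at hazard ratio 0.8 and 50% progression.
- ±2 days (21 to 37 distinct times): ratio 0.986 to 0.998, so about 0.2 to 1.5%. The largest power loss is 26.5 − 25.5 = 1.0 point.
- ±14 days (29 to 108 distinct times): attenuation of at most about 0.2% and no power loss.

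Breslow was nearer 1 in all 36 settings. Measured against the standard error, the largest shift is at hazard ratio 0.5, 50% progression and nominal weeks: (ln 0.5145 − ln 0.4952) / 0.173 = 0.0382 / 0.173 = 0.22 standard errors.

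**Second simulation.** 280 patients, true hazard ratio 0.6, 10% dropout, 600 runs (Breslow vs Efron):
- Whole weeks, 29% events: 0.610 vs 0.600; power 58.2% vs 60.5%.
- Whole weeks, 46% events: 0.627 vs 0.608; power 74.7% vs 79.2%.
- Actual dates within ±2 days: 0.601 vs 0.599; power 59.0% vs 59.7%.

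These agree with the ranges above.

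**The case against.** The strongest reply is that heavy ties are inferred and not documented. A unit of weeks is not a rounding rule. Time runs from each patient's own baseline date, censoring uses evaluation dates, and SAP 5.6 does not move visits to nominal weeks. On that reading the effect nearly vanishes. Breslow is also a recognised method, and code that relies on a default can be reproduced. CDP is not the endpoint that sets the sample size, it is interpreted inferentially only if the primary analysis succeeds, and the log-rank test replaces the Cox test if proportional hazards is rejected.

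Most of this stands, and it limits the point to low severity. It does not settle the time unit. The confirmation rule in SAP 7.4.1 needs a second assessment at or after t + 12 weeks. Counted in exact days, with both visits scattered independently and uniformly over ±2 days (an assumption), 10 of the 25 offset pairs (40%) put the next scheduled visit less than 84 days after onset, too early to confirm. A programmer could reasonably round to whole weeks to make the rule work, and visits within ±2 days would then all fall on the nominal week. Off-schedule EDSS at relapses would break few ties, because relapses are rare. None of the objections gives a reason to prefer Breslow.

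A reader might infer that every event sits on a 12-week grid and that all CDP hazard ratios are therefore materially biased. The date-based definition, the absence of visit windows and the relapse visits do not support that. Code without a TIES option is printed only for the two secondary endpoints, their checks and one gender model; the other CDP analyses inherit it by reference.

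**Conclusion.** The gap is real and small. No tie method is named and the time unit is open, so the default applies and moves the hazard ratio slightly toward 1. With actual dates the log hazard ratio is attenuated by about 0 to 1.5%, with a power loss of at most about 1 point. With times rounded to nominal weeks it is about 1 to 7% and 0 to 6 points, the upper end only at 50% placebo progression by week 48. These ranges rest on assumed event rates, hazard ratios and visit scatter.

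The shift is conservative, so it does not threaten type I error. The larger power losses should not be quoted as the expected effect: they need both rounding and high event rates, and the documents support neither. The SAP does not contradict itself here, and the omission would not by itself be expected to change the trial's conclusion. Label: free improvement, low severity.

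**What to change.** Add TIES=EFRON to every PHREG MODEL statement: the main and proportional-hazards check models in SAP 7.4.1 and 7.4.2, and the gender model in 7.5.21. State that it also applies to 7.5.3, 7.5.4, 7.5.20, the second gender CDP model and the combined Part A and Part B repeats.

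Add one sentence saying that event and censoring times are computed in days from the baseline date to the actual assessment date. State alongside it how the 12-week confirmation gap is counted, since exact days and whole weeks can treat a slightly early visit differently.

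The cost is one option in the code and a sentence or two of text, settled before unblinding. Data collection, sample size and trial conduct do not change.
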